Study design		Using a traditional "3+3" dose-escalation design, subjects will be sequentially assigned to one of three dose groups (2.8×10^{10} units, 1.4×10^{11} units, and 7.0×10^{11} units per dose, once daily, with continuous intranasal instillation for 4 days). Each dose group will include 3 subjects, who will be enrolled one by one. The exploration of the next dose can only proceed if no dose-limiting toxicity (DLT) is observed in the 3 subjects. If 1 out of the 3 subjects experiences DLT, an additional 3 subjects will be enrolled in the same dose group; the exploration of the next dose can only move forward if no DLT is observed in these newly added 3 subjects. A minimum of 6 and a maximum of 18 subjects will be recruited during the dose exploration phase. Patients will receive other standard medical treatments in accordance with the recommendations in the 2022 Chinese Guidelines for Secondary Prevention of Ischemic Stroke and Transient Ischemic Attack , including antiplatelet drugs or anticoagulants, antihypertensive drugs, lipid-lowering drugs, and glucose-lowering drugs.
Outcome Measures	Primary Outcome Measure	Dose-Limiting Toxicity (DLT) Related to hUC-MSC-sEV-001 Includes: (1) Grade 3-4 severe adverse events occurring on day 14 (+-2), graded according to Common Terminology Criteria for Adverse Events (CTCAE) V5.0; (2) NIHSS score increase of ≥ 4 from baseline on day 14 (+-2); NIHSS score assessed by a professional rehabilitation physician;(3) Symptomatic intracranial hemorrhage occurring on day 14 (+-2); detected via CT scan and patient symptom presentation.
	Secondary Outcome Measures:	Serious adverse events related to the investigational drug within 90 (+-7) days. Distribution of Modified Rankin Scale (mRS) Scores within 90 (+-7) days. Barthel Index within 90 (± 7) days. Five-level, five-dimensional EuroQol (EQ-5D-5L) . Proportion of Modified Rankin Scale (mRS) Scores of 0-2 within 90 (+-7) days. All-cause mortality at 90 (+-7) days. Changes in infarct volume at 14 (+-2) days compared to baseline. Change from Baseline in National Institutes of Health Stroke Scale (NIHSS) Score.
Follow-up duration		Baseline (0~1 day), 7 (± 1) days, 14 (± 2) days, 90 (± 7) days
Sample size		6-18 subjects need to be included.

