Single-center, prospective, dose-escalation clinical trial.

(2) Trial Administration Strategy

A traditional "3+3" dose-escalation design will be adopted. Subjects will be sequentially assigned to one of three dose groups (2×10^{10} units, 1×10^{11} units, 5×10^{11} units per administration, once daily for 4 consecutive days via intranasal instillation). Each dose group initially enrolls 3 subjects, with sequential enrollment (i.e., the next subject is enrolled only after the previous subject completes the 14-day DLT observation period).

- If no DLT is observed in 3 subjects of a dose group, the study proceeds to the next higher dose level.

- If 1 out of 3 subjects experiences DLT, an additional 3 subjects are enrolled in the same dose group. If no DLT is observed in the additional 3 subjects, the study proceeds to the next higher dose level; if ≥ 1 additional subject experiences DLT, the current dose level is defined as the maximum tolerated dose (MTD), and dose escalation is terminated.
- A total of 6 to 18 subjects will be recruited during the dose-escalation phase.

(3) Study Suspension or Early Termination

The study will be suspended or terminated early if any of the following occurs:

- Violation of the *Good Clinical Practice (GCP)* or the *Administrative Measures for Stem Cell Clinical Research (Trial)*;
- Emergence of new safety or efficacy data on MSC-sEVs indicating that the trial poses a serious risk to patient safety or is clearly ineffective;
- Failure to enroll subjects as scheduled for 3 consecutive months;
- Major protocol deviations that affect the validity of study data;
- Request for termination by the sponsor or regulatory authorities.

2. Subject Selection Criteria

(1) Inclusion Criteria

- Confirmed diagnosis of acute ischemic stroke (in accordance with the *Chinese Guidelines for the Diagnosis and Treatment of Acute Ischemic Stroke (2023)*);
- Aged 18-70 years, regardless of gender;
- Anterior circulation occlusion (internal carotid artery, middle cerebral artery M1/M2 segment) confirmed by CTA or MRA;
- mRS score of 0-1 before the current stroke episode (indicating no or minimal disability prior to the index event);
- ASPECTS ≥ 6 on non-contrast computed tomography (NCCT) or diffusion-weighted imaging (DWI) after stroke onset (indicating a small to moderate infarct volume);
- NIHSS score ≥ 6 at screening (indicating moderate to severe neurological deficit);

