- Confirmation of the MTD or identification of an unsafe dose level;
- Major flaws in the study design that affect data validity;
- Regulatory requirements (e.g., request by the National Medical Products Administration [NMPA]).

. Subject Withdrawal

Subjects may withdraw from the study at any time for the following reasons:

(1) Investigator-determined withdrawal:

① The subject develops a medical condition that makes continued participation unsafe (e.g., severe allergic reaction, intracranial hemorrhage);② The subject uses medications that interact with the study drug (e.g., immunosuppressants) or affect efficacy assessment (e.g., edaravone);③ The subject experiences a SAE that requires termination of study participation;④ The subject has poor compliance that compromises the reliability of safety or efficacy data.

(2) Subject-initiated withdrawal:

① The subject voluntarily requests to withdraw (no reason required);② The subject is lost to follow-up (no contact for ≥ 2 weeks).

For withdrawn subjects, the investigator shall conduct a final safety assessment (if possible) and document the reason for withdrawal in the CRF. Subjects who withdraw due to AEs/SAEs shall receive appropriate medical treatment, and follow-up shall continue until the AE/SAE resolves or stabilizes.

(7) Criteria for Terminating the Study

The study will be terminated immediately if any of the following occurs:

≥ 2 subjects experience DLT at the same dose level (indicating that the dose exceeds the MTD);

- Production of hUC-MSC-sEV-001 fails to meet quality standards for 3 consecutive batches, resulting in inability to administer scheduled doses;

- The study drug is found to have no clinical benefit (e.g., no improvement in neurological function in all enrolled subjects) or is associated with unexpected severe toxicity;
- A major protocol deviation is identified (e.g., incorrect randomization, unapproved dose modification) that invalidates the study results;
- The sponsor terminates the study due to funding, strategic adjustments, or other reasons;
- The Ethics Committee or NMPA issues an order to terminate the study.

3. Intervention Measures

(1) Trial Drug

- **Generic Name:** Human Umbilical Cord Mesenchymal Stromal Cell-Derived Small Extracellular Vesicle (hUC-MSC-sEV-001) Nasal Drops
- **Source:** Isolated and purified from the supernatant of hUC-MSCs cultured under GMP conditions

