1. Neurological Function Scales:

- **NIHSS:** Assesses the severity of neurological deficits (range: 0-42; higher scores indicate more severe deficits). Administered at baseline, Day 7, Day 14, and Day 90.
- **mRS:** Assesses functional independence (range: 0-6; scores 0-2 indicate good functional outcome). Administered at baseline, Day 7, Day 14, and Day 90.
- **Modified Barthel Index (MBI):** Assesses activities of daily living (range: 0-100; higher scores indicate better independence). Administered at baseline, Day 14, and Day 90.
- **EQ-5D-5L:** Assesses health-related quality of life (including mobility, self-care, usual activities, pain/discomfort, anxiety/depression; scored as a utility value ranging from -0.291 to 1.0). Administered at baseline, Day 14, and Day 90.

2. Cerebral Perfusion Parameters (CTP):

- Measured at baseline, Day 14, and Day 90: cerebral blood volume (CBV), cerebral blood flow (CBF), mean transit time (MTT), time to peak (TTP) in the infarct core and penumbra.
- Changes in perfusion parameters from baseline are used to evaluate the improvement of cerebral blood flow.

3. Infarct Volume Measurement:

- Infarct volume is measured on DWI using the ABC/2 method (A: maximum length, B: maximum width perpendicular to A, C: number of slices × slice thickness).
- Changes in infarct volume from baseline to Day 14 are used to evaluate infarct progression or regression.

5. Outcome Evaluation Indicators

(1) Primary Safety Endpoints

- **Dose-Limiting Toxicity (DLT):** Assessed within 14 days of the first dose, defined as any of the following:
 1. Grade 3-4 AE related to the study drug (CTCAE V5.0), such as severe nasal bleeding, anaphylactic reaction, or hepatic injury;
 2. Increase in NIHSS score ≥ 4 points from baseline (indicating significant neurological deterioration);
 3. Symptomatic intracranial hemorrhage (confirmed by CT/MRI and associated with neurological deterioration).

(2) Secondary Safety Endpoints

1. **SAE Incidence:** Proportion of subjects with drug-related SAEs within 90 days of the first dose;
2. **All-Cause Mortality:** Proportion of subjects who die from any cause within 90 days of the first dose;
3. **Laboratory Abnormality Rate:** Proportion of subjects with Grade ≥ 3 laboratory abnormalities (e.g., thrombocytopenia, elevated liver enzymes) within 90 days.

(3) Efficacy Endpoints

1. **Functional Outcome:** Proportion of subjects with mRS score 0-2 at Day 90;

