
- **Recovery Procedures:**

1. The CRC labels the recoverable study drug with "To Be Recovered" and records the reason in the inventory log;
2. The study drug is returned to the sponsor in insulated containers with dry ice, accompanied by a "Study Drug Recovery Form";
3. The sponsor confirms receipt and issues a "Recovery Confirmation Certificate", which is stored in the study file.

8. Observation and Management of Adverse Events

(1) Definitions

- **Adverse Event (AE):** Any untoward medical occurrence in a subject administered a pharmaceutical product, which does not necessarily have a causal relationship with this treatment. AEs include clinical signs (e.g., abnormal laboratory findings), symptoms, or diseases.
- **Serious Adverse Event (SAE):** An AE that results in death, is life-threatening, requires inpatient hospitalization or prolongation of existing hospitalization, causes persistent or significant disability/incapacity, or is a congenital anomaly/birth defect.
- **Adverse Drug Reaction (ADR):** A response to a drug that is noxious and unintended, and which occurs at doses normally used in humans for the prophylaxis, diagnosis, or therapy of diseases, or for the modification of physiological function.
- **Dose-Limiting Toxicity (DLT):** An AE that is severe enough to prevent dose escalation, as defined in Section 5.1 (Primary Safety Endpoints).

(2) Observation and Recording of Adverse Events

- **Monitoring Period:** From the time of informed consent signing until 30 days after the last dose of the study drug.
- **Reporting Requirements:** Subjects are instructed to report any new symptoms, signs, or discomfort to the investigator immediately. The investigator queries the subject about AEs at each visit using open-ended questions (e.g., "Have you experienced any new symptoms since your last visit?").
- **Documentation:** All AEs are recorded in the "Adverse Event Record Form" in the CRF, including:
 - Onset time, date, and duration;

- Severity (CTCAE V5.0: Grade 1 = mild, Grade 2 = moderate, Grade 3 = severe, Grade 4 = life-threatening, Grade 5 = death);
- Description of signs and symptoms (e.g., "nasal congestion, mild, lasting 2 days");
- Relationship to the study drug (assessed using the five-point scale: definite, probable, possible, unlikely, unrelated);
- Treatment measures (e.g., "normal saline nasal irrigation");
- Outcome (resolved, resolving, stable, worsening, fatal).

(3) Management of Adverse Events

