 - Grade ≥ 3 laboratory abnormalities are summarized as frequency (percentage) by dose group.

(4) Sample Size Justification

This is a phase I dose-escalation study designed to explore the safety and MTD of hUC-MSC-sEV-001. Using the "3+3" design, a sample size of 6-18 subjects is sufficient to identify the MTD with a 90% probability of avoiding overdosing and a 80% probability of identifying the MTD if it exists.

(5) Statistical Software

All statistical analyses are performed using SAS 9.4 software (SAS Institute Inc., Cary, NC, USA). Two-sided tests are used, and a P-value < 0.05 is considered statistically significant.

(6) Interim Analysis

No interim analysis is planned for this study due to the small sample size. The study will be terminated early only if safety concerns arise (e.g., ≥ 2 subjects experience DLT at the same dose level).

12. Quality Control and Assurance

(1) Protocol Compliance

- **Training:** All study personnel (investigator, CRC, monitor, pharmacist) receive training on the study

protocol, GCP, and stem cell clinical research regulations before study initiation. Training records are retained in the study file.

- **Standard Operating Procedures (SOPs):** SOPs are developed for key processes, including subject screening, study drug administration, adverse event reporting, and data management. Study personnel strictly follow the SOPs to ensure consistency.
- **Protocol Deviation Monitoring:** The monitor records all protocol deviations (e.g., missed visits, incorrect dose administration) in the "Protocol Deviation Log". Major deviations are reported to the Ethics Committee and sponsor.

(2) Study Drug Quality Control

- **Manufacturing Quality:** The study drug is produced under GMP conditions, and each batch is tested for purity, potency, sterility, and endotoxin levels. A certificate of analysis (CoA) is provided for each batch.
- **Storage and Transportation:** Temperature monitoring during transportation and storage ensures that the study drug remains within the specified temperature range (-80°C ± 10°C). Temperature records are reviewed and archived.
- **Inventory Management:** The study drug inventory is checked monthly to ensure that the quantity administered matches the quantity received, and to prevent expiration or loss.

(3) Laboratory Quality Control

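### The DLT definition stops at Grade 4, so a drug-related death that meets no other DLT item adds nothing to the 3+3 count

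*Protocol*

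**What the plan says.** Section 5(1) defines a DLT as any one of three things within 14 days of the first dose. Item 1 is "Grade 3-4 AE related to the study drug (CTCAE V5.0), such as severe nasal bleeding, anaphylactic reaction, or hepatic injury". Item 2 is an NIHSS rise of at least 4 points from baseline. Item 3 is symptomatic intracranial hemorrhage confirmed by imaging. The synopsis (Primary Outcome Measure) gives item 1 the same upper limit: "Grade 3-4 severe adverse events occurring on day 14 (+-2").

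The severity scale in Section 8(2) separates the top two grades: "Grade 4 = life-threatening, Grade 5 = death". The general DLT definition in Section 8(1) adds no further event: "An AE that is severe enough to prevent dose escalation, as defined in Section 5.1 (Primary Safety Endpoints").

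Two decision rules use the DLT count:

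- **Escalation, Section 1(2):** "If no DLT is observed in 3 subjects of a dose group, the study proceeds to the next higher dose level". One DLT in three adds three subjects at the same dose.
- **Stopping, Section 2(7):** immediate termination if "≥ 2 subjects experience DLT at the same dose level (indicating that the dose exceeds the MTD"). Section 11(6) repeats the threshold as its example of a safety reason to stop early.

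**The concern.** The DLT count is the stated decision rule of a 3+3 design and, here, also the primary outcome. Item 1 is a closed range that leaves out the worst grade on the protocol's own scale. A related life-threatening reaction counts, while a related death recorded as Grade 5 does not, unless it qualifies by another route.

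If that happened, the cohort could be read as free of DLTs and the written rule would point to a dose five times higher (the levels in Section 1(2) are 2×10^10, 1×10^11 and 5×10^11 per administration). The death would also be absent from the primary safety result. It would appear only in secondary endpoints: drug-related SAEs and 90-day all-cause mortality.

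**Working it through.** **Step 1. Is death in the DLT list by any wording?** Item 1 in Section 5(1) and in the synopsis ends at Grade 4. Items 2 and 3 do not mention death. Section 8(1) refers back to Section 5(1). No other section adds it.

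**Step 2. Is Grade 3-4 the protocol's usual way of writing Grade 3 and above?** Not consistently. The open form, Grade ≥ 3, is used for suspending the drug (Section 3(4)) and for laboratory abnormalities (Sections 5(2) and 11(3)). Section 8(3) uses Grade 3-4 for drug suspension and gives SAEs a separate management rule. The authors had the open form available and did not use it in the DLT item.

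**Step 3. Which related deaths still count?** Those with symptomatic intracranial hemorrhage (item 3), those with a recorded NIHSS rise of 4 or more (item 2), and those with a related Grade 3-4 event on record (item 1). Item 2 depends on a score having been taken. Dosing is on Days 0 to 3 (Section 3(2)) and the first NIHSS scheduled after baseline is Day 7 ± 1 (Sections 4(3) and 6), so the earliest scheduled score is 7 − 1 = Day 6. A death before Day 6 has no post-baseline score unless an unscheduled one is taken.

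**Step 4. Apply the rules.** At one dose level, let k be the number of related deaths that meet no other DLT item, and m the number of other subjects with a DLT.

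- DLT count as written = m
- DLT count with Grade 5 included = m + k

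| Case in the first three subjects | As written | Action by the rule | With Grade 5 | Action by the rule |
|---|---|---|---|---|
| k = 1, m = 0 | 0 of 3 | escalate | 1 of 3 | add 3 at the same dose |
| k = 2, m = 0 | 0 of 3 | escalate | 2 of 3 | stop, Section 2(7) |
| k = 1, m = 1 | 1 of 3 | add 3 at the same dose | 2 of 3 | stop, Section 2(7) |

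Section 1(2) gives no action for two DLTs among the first three, so Section 2(7) has to handle that case, and it uses the same count. The table keeps a subject who died in the cohort of three. These are outcomes of the written rule, not forecasts of what the team would do.

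**Step 5. Sample size.** Three dose levels with at most 3 + 3 = 6 subjects each give 3 × 6 = 18, which reproduces the protocol's maximum. Counting Grade 5 does not change it.

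**The case against.** The best reply is that no trial team would escalate past a drug-related death, and that the protocol gives several reasons why this one would not.

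- **Termination clauses.** Section 2(7) requires immediate termination for severe toxicity that was not expected. Section 9(2) names nasal irritation and allergic reactions as example risks, so many related deaths would qualify. That would stop the trial after one death, whereas counting it as a DLT would only add three subjects. Sections 1(3) and 2(6) also allow a stop, and SAEs are reported within 24 hours. All of this stands and makes unchecked escalation unlikely. But these clauses depend on how the event is classed, have no numerical threshold, and do not put the death into the DLT count.
- **Sequential enrolment.** Under Section 1(2), "the next subject is enrolled only after the previous subject completes the 14-day DLT observation period". A subject who dies on Day 5 never completes that period, so enrolment might simply halt. That is a fair literal reading, and it means the 0 of 3 in the table assumes the subject stays in the cohort. On either reading the death contributes nothing to the numerator.
- **Recording.** Section 8(2) has separate fields for severity and outcome, and fatal is an outcome. A fatal anaphylaxis entered as Grade 4 with fatal outcome would count under item 1. This narrows the gap, but it also means that the same death counts or not according to how the form is filled in.
- **Intent.** The authors very likely meant to include deaths. That supports correcting the wording.
- **Judgement.** Item 1 itself needs a relatedness judgement, so the counted rule is not free of judgement either. True, but once an event is judged related, the count then fixes the action, and the termination clauses do not do that as tightly.

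**Conclusion.** The point holds: the DLT definition is wrong as written. A drug-related death within 14 days that meets no other DLT item adds 0 to the escalation count and 0 to the stop at "≥ 2 subjects experience DLT at the same dose level". One such death moves the reading from 1 of 3 to 0 of 3. Two at one level move it from a mandatory stop to none. One such death plus one other DLT moves it from a stop to adding three subjects.

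This rests on a literal reading of item 1, on the death being recorded as Grade 5 with no separate related Grade 3-4 event, and on no qualifying NIHSS score or hemorrhage. The documents give no rate for such events, so the size is stated in counts and not as a probability. The case is narrow and other safeguards would probably act first, but it concerns the most serious related harm and both the decision rule and the primary endpoint. It should be corrected.

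**What to change.** In Section 5(1), change item 1 to read: *Grade ≥ 3 (including Grade 5) AE related to the study drug (CTCAE V5.0)*. Make the same grade change in item (1) of the synopsis. Leave Sections 1(3), 2(6) and 2(7) unchanged, so that one death can still stop the trial on its own.

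When editing the synopsis, note that it describes events on Day 14 ± 2, while Section 5(1) sets the window as within 14 days of the first dose. That is a separate timing flaw, but the synopsis should follow Section 5(1) so that an early death is covered in both places.

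The cost is a wording amendment to one item in two places, with no new procedures or visits. Up to three extra subjects at a dose level would be needed only if such a death occurred, and these fall within the existing maximum of 18.

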 - **Hematology:** Complete blood count (CBC) with differential (red blood cell [RBC], hemoglobin [Hb], white blood cell [WBC], neutrophil percentage [NEUT%], lymphocyte percentage [LYMPH%], platelet count [PLT]);
 - **Clinical Chemistry:** Liver function (ALT, AST, total bilirubin [TBIL], alkaline phosphatase [ALP], γ -glutamyl transferase [γ -GT]), renal function

(Scr, BUN), fasting blood glucose (FBG), glycated hemoglobin (HbA1c), lipid profile (total cholesterol [TC], triglycerides [TG], HDL, LDL, lipoprotein (a) [LP(a)]);

- **Coagulation Function:** PT, INR, APTT, thrombin time (TT), fibrinogen (FIB);
- **Serum Electrolytes:** Potassium (K⁺), sodium (Na⁺), calcium (Ca²⁺), magnesium (Mg²⁺), phosphorus (P³⁺), chlorine (Cl⁻);
- **Infectious Disease Screening:** HBsAg, hepatitis B surface antibody (HBsAb), hepatitis B e antigen (HBeAg), hepatitis B e antibody (HBeAb), hepatitis B core antibody (HBcAb), HCV antibody, HIV antibody, TPPA, RPR;
- **Tumor Markers:** Alpha-fetoprotein (AFP), carbohydrate antigen 199 (CA199), carcinoembryonic antigen (CEA);
- **Urinalysis:** Urine protein (PRO), urine glucose (GLU), quantitative urine RBC, quantitative urine WBC, urine ketones (KET);
- **Pregnancy Test:** Urine pregnancy test for women of childbearing potential at screening and Day 90.

3. Imaging Examinations:

- **Chest X-ray:** Performed at screening and Day 90 (to exclude active pulmonary infection or malignancy);
- **Electrocardiogram (ECG):** 12-lead ECG performed at screening, Day 14, and Day 90 (to evaluate cardiac function and detect arrhythmias);
- **Cerebral Imaging:**
 - Baseline: NCCT, DWI, MRA/CTA (to confirm infarct location and vascular occlusion);
 - Day 14 and Day 90: DWI, fluid-attenuated inversion recovery (FLAIR), CTA/CT perfusion (CTP) (to assess infarct volume, edema, and cerebral perfusion).

4. Adverse Events Monitoring:

- AEs are monitored from the time of informed consent signing until 30 days after the last dose of the study drug.
- All AEs (including nasal irritation, headache, rash) are documented in the "Adverse

Event Record Form" in the CRF, with details including onset time, severity (CTCAE V5.0), duration, relationship to the study drug (definite, probable, possible, unlikely, unrelated), treatment measures, and outcome.

- SAEs are reported to the Ethics Committee, sponsor, and NMPA in accordance with regulatory requirements (within 24 hours of awareness).

(3) Efficacy Observation Indicators

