2. Efficacy Assessments:

- Neurological scales: NIHSS, mRS, MBI, EQ-5D-5L;
- Infarct volume measurement (DWI) and CTP parameter analysis.

3. Documentation: Record combined medications, rehabilitation therapy, and schedule the Day 90 visit.

Fourth Visit (Day 90 ± 7)

1. Safety Assessments:

- Vital signs measurement;
- Laboratory tests: CBC, clinical chemistry, coagulation function, serum electrolytes, infectious disease screening, tumor markers, urinalysis, pregnancy test (if applicable);
- Imaging examinations: Chest X-ray, 12-lead ECG, DWI, FLAIR, CTA/CTP;
- Final AE follow-up (until 30 days after the last dose).

2. Efficacy Assessments:

- Neurological scales: NIHSS, mRS, MBI, EQ-5D-5L;
- Final infarct volume measurement and CTP parameter analysis.

3. Study Completion: Confirm completion of all assessments, and document any protocol deviations.

Items/Visits	Baseline (Day 0)	Day 7 (±1)	Day 14 (±2)	Day 90 (±7)
Sign Informed Consent Form	●			
Review Inclusion/Exclusion Criteria	●			
Collect Demographic & Clinical Data	●	●	●	●
Vital Signs	●	●	●	●
Urine Pregnancy Test	●			●
Hematology (CBC) *	●	●	●	●
Clinical Chemistry (Liver/Kidney Function, Glucose, Lipids) *	●	●	●	●
Coagulation Function (PT, INR, APTT, FIB)	●		●	●
Serum Electrolytes	●		●	●
Infectious Disease Screening (8 Items)	●		●	●
Tumor Markers (AFP, CA199, CEA) *	●		●	●
Urinalysis *	●	●	●	●

Items/Visits	Baseline (Day 0)	Day 7 (±1)	Day 14 (±2)	Day 90 (±7)
Chest X-ray	•		•	
12-Lead ECG	•		•	•
Cerebral Imaging (CT/MRI/CTA/CTP)	•	•	•	•
Neurological Scales (NIHSS, mRS)	•	•	•	•
Modified Barthel Index (MBI)	•		•	•
EQ-5D-5L Score	•		•	•
Record Adverse Events	•	•	•	•
Record Concomitant Medications	•	•	•	•
Record Rehabilitation Therapy	•	•	•	•

7. Regulations for Packaging, Acceptance, Storage, Distribution, and Recovery of Study MSC-sEV Preparations

(1) Packaging of Study MSC-sEV Preparations

- **Primary Packaging:** Sterile glass vials (2.0 mL) with rubber stoppers and aluminum caps, labeled with the study drug name, batch number, dose level, expiration date, storage conditions, and "For Clinical Trial Use Only".
- **Secondary Packaging:** Individual cartons containing one vial of study drug and one vial of hyaluronidase, with a leaflet describing the administration method.
- **Tertiary Packaging:** Insulated containers with dry ice for transportation, labeled with "Biological

Product", "Keep Frozen (-80°C)", and the sponsor's contact information.

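### The protocol contradicts itself on whether adverse events are recorded to Day 33–34 or to Day 90, so a non-serious event first found at Day 90, such as a silent bleed on the safety scan, may go unrecorded

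*Protocol*

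**What the plan says.** **Text that stops AE recording early.** Section 4(2), Adverse Events Monitoring: "AEs are monitored from the time of informed consent signing until 30 days after the last dose of the study drug". Section 8(2) gives the same monitoring period. Section 6, Fourth Visit, repeats the limit at the Day 90 visit itself: "Final AE follow-up (until 30 days after the last dose").

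**Text that carries AE assessment to Day 90.** The Research Methods section places safety assessment, including adverse reactions, at baseline and at Days 7, 14 and 90. Section 8(2) has the investigator ask about AEs at every visit. The schedule table in section 6 marks AE recording in all four visit columns.

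**What the 90-day safety endpoints count.** Section 5(2) lists three:
- "Proportion of subjects with drug-related SAEs within 90 days of the first dose"
- deaths from any cause within 90 days
- Grade 3 or higher "laboratory abnormalities (e.g., thrombocytopenia, elevated liver enzymes) within 90 days"

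**Where hemorrhage appears.** Section 2(2) excludes any intracranial hemorrhage, including hemorrhagic transformation, at entry. Section 2(6) gives intracranial hemorrhage as an example reason for withdrawal. As an outcome it appears once, in the definition of dose-limiting toxicity (DLT). Section 5(1) has "Symptomatic intracranial hemorrhage (confirmed by CT/MRI and associated with neurological deterioration"), within 14 days of the first dose. The summary has it "detected via CT scan and patient symptom presentation" at Day 14 (±2).

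**Imaging.** Section 6 lists DWI, FLAIR and CTA/CTP among the safety assessments at Days 14 and 90.

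**The concern.** A monitoring period that closes at about Day 33 does not fit a visit at Day 83–97 that repeats laboratory tests, ECG and brain imaging for safety. Staff who follow the text would not record a new non-serious finding at that visit. Staff who follow the table would. The contradiction touches every type of event.

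Intracranial hemorrhage shows best what is at stake. The protocol treats bleeding as a hazard: it excludes it at entry, makes symptomatic bleeding a DLT, and discourages NSAIDs because of bleeding risk in section 3(4). A bleed without symptoms that arises after the Day 14 scan would normally first be seen on the Day 90 scan. If it is not entered as an AE, no other endpoint picks it up, and a later analysis plan cannot recover what the case report form did not collect. Safety is part of the primary objective, so the record should not depend on which sentence the site happens to follow.

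**Working it through.** The protocol states no figure to reproduce. The check is day arithmetic, then a comparison of endpoints.

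**1. AE cut-off under the 30-day text.**
- Section 3(2) doses on Days 0 to 3, so the cut-off is 3 + 30 = Day 33.
- The summary's treatment plan can be read as a last dose on Day 4, so the cut-off is 4 + 30 = Day 34.

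**2. Distance from the cut-off to the Day 90 visit.** The window is 90 ± 7, or Day 83 to 97.
- Cut-off Day 33: 83 − 33 = 50 to 97 − 33 = 64 days.
- Cut-off Day 34: 83 − 34 = 49 to 97 − 34 = 63 days.

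So every Day 90 visit falls 49 to 64 days after AE recording has closed.

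**3. Interval without a scan.** The Day 14 scan falls on Day 12 to 16, and none is scheduled between it and the Day 90 scan.
- Interval: 83 − 16 = 67 to 97 − 12 = 85 days.
- Part of it inside the AE window: 33 − 16 = 17 to 34 − 12 = 22 days.

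A silent bleed arising in this interval has no scheduled scan to reveal it until after the cut-off.

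**4. Where a non-serious, asymptomatic bleed first seen on the Day 90 scan would be counted.**

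| Route | Counted? | Reason |
|---|---|---|
| DLT, 5(1) | No | Needs neurological deterioration; closes at Day 14–16 |
| Drug-related SAEs to 90 days, 5(2) | No | Not serious |
| Deaths to 90 days, 5(2) | No | Not fatal |
| Grade ≥3 laboratory abnormalities, 5(2) | No | An imaging finding |
| AE incidence by dose, 11(3) | Contradictory | Closed under the 30-day text; open under the table, the each-visit query and Research Methods |
| Withdrawal reason, 2(6) | No | First seen at the last visit |

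Section 13(2) does not close the gap. It lists the safety results as AE/SAE incidence, DLT and laboratory abnormalities, and the imaging results as infarct volume and perfusion.

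**5. The same bleed seen on the Day 14 scan.** It lies inside the AE window on either reading. Section 8(2) has each AE described individually, so it can be counted by dose. The gap is therefore confined to Day 90.

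**6. What a count could tell.** The exact (Clopper-Pearson) upper 95% limit for zero events in n subjects is 1 − 0.025^(1/n).
- n = 3: 1 − 0.025^(1/3) = 0.708
- n = 6: 1 − 0.025^(1/6) = 0.459
- n = 18: 1 − 0.025^(1/18) = 0.185

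No event rate is assumed, because the protocol gives none.

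**The case against.** The strongest case is that little is lost. Serious drug-related bleeds and deaths are already counted to Day 90, and the SAE incidence in 11(3) is not limited to related events. Bleeds seen before the cut-off are AEs. What remains is a non-serious finding about 80 or more days after a four-day course. It would change no escalation decision, since the DLT window has long closed. If AE recording at Day 90 stands, as the table and two other places suggest, such a bleed is an ordinary AE and no separate endpoint is needed. Most of this stands. It is why the remedy is to settle the AE window and leave the DLT definition alone.

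The texts might also be reconciled by taking the Day 90 entry to mean follow-up of AEs that began earlier, since 8(6) follows AEs until they resolve or stabilize. That reading is possible, but it leaves a newly found event unrecorded.

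A reader might infer three stronger things, and the protocol supports none of them:
- *That asymptomatic hemorrhage has no route at all into the safety results.* The route is contradictory at Day 90 and open before the cut-off.
- *That follow-up scans are not read for blood.* Their stated purpose is "to assess infarct volume, edema, and cerebral perfusion", without hemorrhage. But the baseline purpose, "to confirm infarct location and vascular occlusion", omits it too, although baseline CT or MRI must exclude hemorrhage.
- *That the DLT component is wrong.* Symptomatic hemorrhage within 14 days is a sensible event for escalation decisions.

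**Conclusion.** The point holds as a contradiction in the AE recording period. Three places close it at Day 33–34, and three carry AE assessment to Day 90. Under the first reading, a non-serious event first found at Day 83–97 is not recorded and falls in none of the 90-day safety endpoints. Asymptomatic intracranial hemorrhage on the Day 90 scan is the clearest case, because that scan is ordered for safety.

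The number of Day 90 scans affected is at most 6 to 18, one per subject. That assumes no deaths, withdrawals or losses; section 2(4) withdraws subjects whose stroke worsens, so the true number may be lower. The conclusion rests on the written day limits and on no assumed bleeding rate.

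The gain from correcting it is real but small. It settles which safety data are collected. It cannot test or rank doses: there is no untreated control, and each dose has only 3 to 6 subjects. With an upper limit of 71% for 0/3, and 19% at best for 0/18, a zero count would not be reassurance.

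**What to change.** 1. In 4(2), section 6 (Fourth Visit) and 8(2), run AE monitoring from consent through the Day 90 (±7) visit. This brings the text into line with the schedule table and Research Methods, and covers late findings of every kind.
2. In 4(2), add: *Any intracranial hemorrhage not seen at baseline that appears on the Day 14 or Day 90 scan is recorded as an AE, whether or not symptomatic, with the imaging modality used.*
3. In 11(3), summarize such hemorrhage as frequency (percentage) by dose group. Show symptomatic cases separately, defined as confirmed on CT or MRI with neurological deterioration and without the 14-day limit. Make no between-dose test, and give exact confidence limits if any interval is shown.

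The DLT definition and its 14-day window, the visits and the scan schedule stay unchanged.

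The cost is some extra AE recording after Day 33–34, one field on the form for scans already scheduled, and one table. The counts will be very imprecise and uncontrolled. Section 4(2) lists NCCT, DWI and MRA/CTA at baseline but DWI, FLAIR and CTA/CTP at follow-up, so a small bleed may be missed or may wrongly appear new. Recording the modality makes that visible but does not remove it.
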